### **2. Précis/Abstract:**

The goal of the proposed research is to determine whether riluzole, a drug that increases glutamate reuptake, will decrease CNS glutamate in breast cancer survivors with increased inflammation and fatigue. We will also determine whether decreasing glutamate with riluzole will reverse inflammation-related fatigue and other symptoms including cognitive dysfunction and decreased motivation. To accomplish these goals, we plan to conduct an 8 week, double-blind, randomized control trial of riluzole (100 mg/d) versus placebo in 40 breast cancer survivors (n=20 per group). All breast cancer survivors will have completed treatment within 1-5 years and have a fatigue level of  $\geq 4$  (on a 10 point scale) and a plasma c-reactive protein (CRP) concentration  $>3\text{mg/L}$  (indicative of high inflammation). Patients will undergo magnetic resonance spectroscopy (MRS) to measure CNS glutamate before and after 1 and 8 weeks of riluzole or placebo treatment. Fatigue and other behavioral assessments including measures of cognitive function, motivation, and startle reactivity will be conducted before and after treatment and correlated with the change in CNS glutamate.

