Thus, CNS glutamate may serve as a final common pathway to CNS pathology and behavioral and cognitive disturbances in breast cancer patients after treatment. Interestingly, memantine, a drug that antagonizes glutamate signaling was found to preserve cognition in cancer patients undergoing whole brain radiotherapy, indicating that blocking glutamate may have neuroprotective effects under conditions of an increased inflammatory load. Taken together, these data suggest that glutamate may be an outstanding target for reversing the behavioral pathology associated with inflammation during breast cancer and its treatment. Demonstration that targeting glutamate to reverse fatigue and cognitive changes in patients with high inflammation and could potentially help treat the long-term toxicities of breast cancer and its treatment. The goal of the current proposal is to test the hypothesis that reduction of glutamate in breast cancer survivors with fatigue and high inflammation will be associated with decreased CNS glutamate and decreased symptoms of fatigue and cognitive function including anhedonia and psychomotor slowing. To test these hypotheses the following aims are proposed:

**Aim 1: To study the impact of 8 weeks of riluzole treatment on CNS glutamate concentrations in breast cancer patients with increased fatigue and high inflammation.**

Using a double-blind randomized controlled trial design, 40 female breast cancer patients with increased fatigue ( $\geq 4$  on a 10 point scale) and high inflammation (CRP $>3$ mg/L) will be treated for 8 weeks with either riluzole or placebo (n=20 per group). At baseline and at 1 and 8 weeks of treatment, all subjects will undergo single voxel MRS to measure CNS glutamate. Voxels will be placed in the right and left basal ganglia and the dACC. In addition, chemical shift MRS imaging will be employed to explore potential glutamate changes in other brain regions of interest.

**Hypothesis 1:** Breast cancer patients administered riluzole will exhibit greater decreases in basal ganglia and dACC glutamate compared to women treated with placebo.

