## **6. Study design and methods:**

### **Participant Selection**

Breast cancer research participants will be referred by physicians in the Glenn Family Breast Center at Winship Cancer Institute of Emory University, recruited through social media campaigns, or recruited through letters from the Georgia Center for Cancer Statistics. We plan to enroll 120 female breast cancer patients between the ages of 21-65 inclusive (to obtain 40 patients with analyzable data). All breast cancer patients will have completed surgery (lumpectomy or mastectomy) with or without neoadjuvant or adjuvant chemotherapy and with or without radiation between 1-5 years prior to enrollment.

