### **Participants**

40 female patients with Stage I-III breast cancer that are between 1-5 years post treatment and are between the ages of 21 and 65, unless otherwise approved by the PI, will be enrolled in this clinical trial. Participants will have completed surgery (lumpectomy or mastectomy) with or without neoadjuvant or adjuvant chemotherapy and with or without radiation. Subjects must have a CRP > 3mg/L and a Single Item Screening Scale for Fatigue score of  $\geq 4$  (out of 10 points, 0 being no fatigue and 10 being severe, incapacitating fatigue) to be eligible for the trial. Based on projections that ~50% of recruited subjects will have a CRP > 3mg/L and a Fatigue score  $\geq 4$  and ~20 of subjects will drop out during the clinical trial, we anticipate that we will need to recruit 120 subjects to yield analyzable data for 40 breast cancer subjects. No patients will be enrolled from vulnerable populations, including neonates, children, prisoners, or institutionalized individuals. No use will be made of fetal tissue. Potential subjects will be excluded for a number of medical conditions that might represent a risk for riluzole (including history of allergic reaction to riluzole and evidence of liver disease) and potentially confound the relationship among CNS glutamate, inflammation and behavior/cognition, including autoimmune or inflammatory disorders, chronic infectious diseases (e.g. HIV, hepatitis B or C), pregnancy, neurologic disorders (including a history of serious head trauma or seizures), liver disease (as manifested as an elevation in liver transaminases) and uncontrolled cardiovascular, metabolic, pulmonary or renal disease (as determined by medical history and laboratory testing). Subjects with a current or past history of schizophrenia will also be excluded. Subjects with Bipolar Disorder that have experienced a manic episode within 6 months of study entry will be excluded or at the PI's discretion. Subjects receiving antidepressants, mood stabilizers, antipsychotic medications or

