**Riluzole Flowchart:**

### **Randomization**

Subjects will be randomized to 100 mg of riluzole (50 mg po BID) or an identical appearing placebo in a 1:1 fashion with no stratification. Subjects will be instructed to take the study medication on an empty stomach (1 hour before or 2 hours after meals). The dosage of riluzole is based on several clinical trials that have previously used this medication to treat a number of psychiatric disorders ranging from depression to generalized anxiety disorder as well as ALS.[31] A randomly generated sequence of assignments to riluzole or placebo will be created and maintained by the study pharmacist. Subjects will be randomized in blocks of 4. If a subject drops out prior to receiving the first dose of medication, she will not be included in data analyses and her randomization assignment will “roll over” to the next recruited subject until 40 subjects have received at least one dose of medication or placebo.

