### **Compliance**

Patients will be asked to fill out a medication log and bring in their pill bottles at each study visit. Patients who have taken less than 75% of their medication may be excluded from study participation. If study removal occurs at or after the Week 4 study visit, the patient will undergo exit safety laboratory testing and physical examination.

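### Accrual stops at 40 dosed, yet 40 is also the number analysable after dropout and the number in the power statement; post-dose loss would leave fewer than 40 Week 8 scans

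*Combined protocol and SAP*

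**What the plan says.** The combined protocol and SAP uses 40 in three ways.

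- **Number dosed.** Section 6, Randomization, runs accrual "until 40 subjects have received at least one dose of medication or placebo". An assignment rolls over to the next woman only when someone leaves before the first dose. No section replaces anyone who leaves later. The Précis ("versus placebo in 40 breast cancer survivors (n=20 per group") and section 5, Aim 1 ("will be treated for 8 weeks with either riluzole or placebo (n=20 per group") also use 40 for the number treated.
- **Number analysable after dropout.** Section 6, Participant Selection, plans 120 women "to obtain 40 patients with analyzable data". Participants assumes that about half of recruits meet the CRP and fatigue criteria and that about "20 of subjects will drop out during the clinical trial", and concludes "we anticipate that we will need to recruit 120 subjects to yield analyzable data for 40 breast cancer subjects". The same section opens by saying that 40 patients, "unless otherwise approved by the PI, will be enrolled in this clinical trial".
- **Number in the power statement.** Section 11 takes a sample size of 40 and mentions no loss.

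The term analysable is not defined. Spectroscopy is done at Baseline 1, Week 1 and Week 8. Aim 1, on which section 11 bases the sample size, concerns 8 weeks of treatment.

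**The concern.** A number that remains after dropout cannot also be the number that starts treatment unless nobody is lost in between. If accrual stops at 40 dosed and some of those women leave before Week 8, the trial has fewer than 40 scans at the time point that Aim 1 is about, while section 11 still quotes power for 40. The plan does provide for leaving after dosing. Compliance sets out what happens "If study removal occurs at or after the Week 4 study visit", and the stopping rules in section 12 discontinue participants for events on treatment.

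**Working it through.** **Step 1. Reproduce the recruitment figure.** Inputs from Participants: 120 recruited, about 50% eligible, dropout of about 20, 40 analysable. The text as available prints no unit for the dropout figure, and a percent sign may have been lost when the PDF was read, so both readings are tried.

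- 20 as a count: 120 × 0.5 − 20 = 40. This reproduces the plan exactly.
- 20% of those eligible: 40 / 0.8 = 50, and 50 / 0.5 = 100 recruits, not 120. Equivalently, 120 × 0.5 × 0.8 = 48 analysable, not 40.
- 40 inflated by 20%: 48 / 0.5 = 96 recruits.
- 50% and 20% both taken from recruits: 40 / 0.3 = 133 recruits.

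Only the count reading returns 120. It implies a loss of 20 out of 60 eligible, or one third.

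**Step 2. Apply the loss to 40 dosed, supposing that it all falls after dosing.**

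- One third: 40 × (1 − 20/60) = 26.7, about 27 at Week 8.
- 20%: 40 × 0.8 = 32.
- No post-dose loss: 40.

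**Step 3. Credit the Week 1 scans.** Section 10 plans a mixed model for repeated measures adjusted for baseline, so a woman scanned at Week 1 but not at Week 8 still contributes. Assumptions: all 40 have a Week 1 scan, and every pair of visits has the same correlation r. The documents give no correlation, so r = 0.5 and r = 0.7 are used. After baseline adjustment, the Week 1 to Week 8 correlation is p = r/(1 + r), which is 0.333 or 0.412. With n per arm at Week 8 and SD σ:

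variance of an arm's Week 8 mean = σ² × (1 − r²) × [(1 − p²)/n + p²/20]

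The effective total N is 2 divided by the square bracket. The ratio of detectable differences is the square root of (bracket / 0.05), because the bracket is 1/20 = 0.05 when all 40 are scanned.

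| Week 8 scans | r | Bracket | Effective N | Ratio to N = 40 |
|---|---|---|---|---|
| 32 (16 per arm) | 0.5 | 0.0611 | 32.7 | 1.11 |
| 32 | 0.7 | 0.0604 | 33.1 | 1.10 |
| 26.7 (13.3 per arm) | 0.5 | 0.0722 | 27.7 | 1.20 |
| 26.7 | 0.7 | 0.0708 | 28.3 | 1.19 |

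With a t reference distribution the ratios are 1.11 for 32 and 1.21 to 1.22 for 27. The detectable Week 8 difference in SD units (two-sided 0.05, 80% power) is then 0.79, 0.88 and 0.96 for 40, 32 and 27 scans at r = 0.5, and 0.65, 0.72 and 0.79 at r = 0.7.

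**Step 4. Sensitivity.** The Week 1 scans help materially only if p is high. At p = 0.8 the effective N would be 36.7 and 33.9 in place of about 33 and 28.

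**The case against.** The best defence is that the passages can be reconciled. Participant Selection uses enrolment for all 120. Baseline 1 with its scan, an optional startle study and Baseline 2 all come before treatment is under way. So 120 recruited, 60 eligible, 20 lost before the first dose and 40 dosed is a coherent sequence, and the plan's own sum does take the 20 from the 60. Randomization also excludes pre-dose leavers from analysis, which hints that the analysed set is everyone dosed.

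That reading is possible, and it is why the shortfall is conditional. It is strained because the dropout is placed during the clinical trial, and the same section says that 40 will be enrolled in that trial. If analysable only means dosed, section 6 (Metabolite Spectral Fitting) stands in the way: it limits the analysis to spectra with CRLB below 25, so a dose alone does not give a usable value.

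The defence is also right that the documents do not forecast a rate of post-dose loss. The compliance and stopping rules are conditional, and the count of post-randomisation dropouts in the DSMB report is a routine item that could include women who leave before dosing. A reader might infer from these that a shortfall is certain; they show only that post-dose loss is provided for.

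It is fair, too, that section 10 does not restrict the model to Week 8 completers. Step 3 allows for that.

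**Conclusion.** The inconsistency stands. As written, the plan delivers its 40 only if there is no loss after dosing, or if analysable means dosed at least once. If the expected loss is post-dose, about 27 women have Week 8 spectroscopy at the rate that the plan's recruitment sum implies, or 32 if the dropout figure means 20%. The detectable Week 8 difference is then about 20% or 10 to 11% larger than with 40. Those percentages rest on equal correlations of 0.5 to 0.7 and complete Week 1 scans, neither of which comes from the documents.

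Three stronger inferences are not supported.

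- That 27 is a worst case or the lower end of a range. Removals for low adherence and spectra failing the CRLB limit have no stated rate, so 27 is not a floor, although Metabolite Spectral Fitting reports low CRLB values in earlier studies.
- That the recruitment sum is wrong. With the count reading it is exact.
- That this point shows the effect size of 0.5 in section 11 to be unsupported at 40. That is a separate matter and adds no weight here.

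The plan should be corrected before its power statement is relied on. Confidence is medium, because the timing of the loss is not stated.

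**What to change.** - Give 40 one meaning, the number dosed, in the Précis, section 5, section 6 (Participant Selection, Participants, Randomization) and section 11.
- State the dropout assumption with its unit (count or percentage) and its timing (before or after the first dose).
- Define analysable, including how spectra that fail the CRLB limit are counted, and restate the expected number with usable Week 8 spectroscopy.
- In section 11, quote the power or detectable effect for that number under the planned baseline-adjusted mixed model, with the assumed correlation stated.

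The cost is wording and one recalculation. The number treated and the visit schedule do not change.

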### **Compliance**

Patients will be asked to fill out a medication log and bring in their pill bottles at each study visit. Patients who have taken less than 75% of their medication may be excluded from study participation. If study removal occurs at or after the Week 4 study visit, the patient will undergo exit safety laboratory testing and physical examination.

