### **Description of Study Procedures (Baseline 1, Startle Study, Baseline 2 and Weeks 1-8)**

All eligible participants with a CRP>3mg/L and a Fatigue Score  $\geq 4$  will complete Baseline 1, be randomized to receive riluzole (100 mg/d) or placebo at Baseline 2, and proceed to study visits at Weeks 1, 2, 4, and 8.

During the Baseline 1 visit and on Week 1 and Week 8, subjects will undergo magnetic resonance spectroscopy (MRS). Between baseline 1 visit and baseline 2 visit, participants will have the option of undergoing a parallel Startle Test Study protocol. This protocol will consist of either 1 or 2 visits, for completing psychiatric assessments and self-report forms and for completing a psychophysiological startle task. A schedule of all assessments is provided in Table 1. Approximately 30 mL of blood will be drawn at the same time of day between 8-10AM (to reduce potential circadian effects) under sterile conditions at Baseline 1 and 2 and Weeks 1, 4 and 8. Screening/safety labs are not time dependent. Safety labs will be completed at Baseline 2, Week 4 and Week 8. At each visit, self-report forms with urine toxicology will occur as well as recording of concomitant medications and adverse events. Neurocognitive testing will be completed on Baseline 1, Baseline 2 and Week 8. Where indicated, participants will be administered the neurocognitive tests and the scanning sequence of the MRS will be completed based on scanner availability and at the discretion of the PI or PI's designee. Subject will be read MRI instructions 48hrs prior to Baseline 1, Week 1, and Week 8 visits to have the subject avoid specific foods, medications, alcohol and cigarettes starting 24hrs prior to the MRS scan. A light lunch/snack may be provided after the fasting lab work.

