## 10. Statistical Analysis:

**Aim 1: To study the impact of 8 weeks of riluzole treatment on CNS glutamate concentrations in breast cancer patients with increased fatigue and high inflammation.**

**Hypothesis 1:** Breast cancer patients administered riluzole will exhibit greater decreases in basal ganglia and dACC glutamate compared to women treated with placebo.

Mixed-effects models for repeated measures (MMRM) will be employed to examine effects of group, time and their interaction on left and right basal ganglia glutamate or dACC controlling for baseline glutamate concentrations in separate analyses for each brain region. Relevant covariates including age, sex, race (white/non-white) and body mass index (BMI), socioeconomic status (as measured by household income), educational status, tumor stage, tumor receptor status (where appropriate), timing (adjuvant versus neoadjuvant) of chemotherapy and radiation (yes/no) will be sequentially tested in the models for goodness of fit (Akaike Information Criterion) and included as appropriate.

**Aim 2: To determine whether decreased CNS glutamate correlates with improved symptoms of fatigue and cognition dysfunction.**

**Hypothesis 2:** Decreased glutamate in the basal ganglia will be associated with decreased fatigue and improved motivation and processing speed. Decreased glutamate in the dACC will be associated with improved executive function and memory performance.

Random intercept linear mixed models will be used to assess whether change in left or right basal ganglia or dACC glutamate predict change in fatigue scores or change in neurocognitive function over time. Models will be adjusted for relevant clinical covariates (including IDS-SR, PSQI, BAI) as indicated above. Separate analyses will be run for each behavioral outcome (MFI, PROMIS) as well tests of cognition (HVLT-R, TMT PASAT COWAT RT FTT, RTT, and DSST) and motivation (DDT, EEfRT, Subjective Value Task, Effort and Delay Task, Daily Assessment/Mobile App Task, Gamble Task, and Go No-Go Variant Task.). Type I errors as a result of multiple testing will be controlled by using a step down Bonferroni procedure.[68]

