## 12. Potential Study Risks:

**Main Riluzole Study Risks:** There are 4 major areas of potential risk in the proposed study stemming from 1) neuropsychiatric assessments, 2) blood drawing, 3) MRS scanning and 4) riluzole treatment. Neuropsychiatric assessments may uncover unpleasant feelings about the subject's present emotional state. The risks of blood drawing include discomfort, bruising, infection, bleeding and fainting. Undergoing MRS scan poses no more risk than undergoing a routine MRI scan. Nevertheless, physical discomfort due to lying in the scanner, occasional headaches due to scanner sounds and previously unrecognized claustrophobic attacks are the

prominent adverse effects of the procedure. Major complications of riluzole (Rilutek) include an allergic reaction to riluzole or the components of the tablet and hepatic toxicity. Riluzole is contraindicated in individuals who have a history of hypersensitivity reactions to riluzole or any of the tablet components and in individuals who have hepatic disease or who have baseline transaminases greater than 3 times the upper limit of normal. The drug is also contraindicated in women who are pregnant. Subjects of childbearing ability must agree, with the study doctor or PI's designee, on a method of birth control to use throughout the study. To ensure no contraindications with alcohol, participants will be told not to consume more than 1 alcoholic drink per day while on study medication (12 fl oz of beer, 5 fl oz of wine, 1.5 fl oz shot of distilled spirit, and also not to consume any alcohol within 24 hours of a study visit brain scan. Of the most commonly observed adverse events associated with the use of RILUTEK in 1,396 individuals with amyotrophic lateral sclerosis, those reported more frequently than with placebo treatment were: asthenia, nausea, elevations in liver function tests, dizziness, decreased lung function, diarrhea, abdominal pain, pneumonia, vomiting, vertigo, circumoral paresthesia, anorexia and somnolence. Table 2 shows the most common treatment-emergent adverse reactions considered possibly related to medication and for which the incidence was  $\geq 1\%$  in an open label Phase IV confirmatory trial for amyotrophic lateral sclerosis of 414 patients.

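### Removal from the study for taking under 75% of medication leaves Week 8 MRS, fatigue and cognitive outcomes uncollected, possibly at different rates by arm

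*Combined protocol and SAP*

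**What the plan says.** Section 6, Compliance, describes the check on adherence: "Patients will be asked to fill out a medication log and bring in their pill bottles at each study visit". The rule follows: "Patients who have taken less than 75% of their medication may be excluded from study participation". Stopping rules in Section 12 repeats it. Neither place says over what period the 75% is counted, who decides, or on what grounds a woman below the threshold is kept or removed.

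The only procedures attached to removal are these: "If study removal occurs at or after the Week 4 study visit, the patient will undergo exit safety laboratory testing and physical examination". Nothing in the plan provides an exit scan, exit fatigue or cognitive testing, or continued outcome visits after removal.

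Table 1 places MRS at Baseline 1, Week 1 and Week 8. Self-report fatigue forms are completed at both baselines and at Weeks 1, 2, 4 and 8. Cognitive testing is at the two baselines and Week 8 only.

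On who is analysed, Randomization sets aside only women who drop out before the first dose, and continues "until 40 subjects have received at least one dose of medication or placebo". Section 10 gives the Aim 1 analysis: "Mixed-effects models for repeated measures (MMRM) will be employed to examine effects of group, time and their interaction". It contains no as-randomised statement, no missing-data assumption and no sensitivity analysis for women who leave.

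**The concern.** Low adherence arises after randomisation, and treatment can cause it. Section 12 lists riluzole effects from the ALS programme: "those reported more frequently than with placebo treatment were: asthenia, nausea, elevations in liver function tests, dizziness". Table 2 adds nausea (6%) and fatigue (4%) as possibly related to the drug in an open-label study. A woman who feels sick or more tired may take fewer tablets, fall below 75% and be removed. Removal could then be more common on riluzole and linked to how she is doing, and fatigue is itself an outcome. Because the rule is discretionary and has no stated criteria, the decision can also follow her clinical course.

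If so, the Week 8 comparison is between women who tolerated the tablets rather than between the groups as randomised. Aim 1 concerns 8 weeks of treatment, so Week 8 is the scan that matters most. Cognition has no other post-treatment assessment. With 20 women per arm, a few removals also cost precision.

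**Working it through.** **1. What is lost, by time of removal (Table 1 against the Compliance paragraph).**
- Removed at Week 1, 2 or 4: no Week 8 MRS, fatigue or cognitive result. The Week 1 scan and any fatigue forms already completed remain, up to three on-treatment forms if removal is at Week 4.
- Low adherence first found at Week 8: that visit's data need not be lost; the text is unclear.

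**2. The plan's own figure.** Section 11 states 80% power for d = 0.5 with N = 40 and alpha 0.05. A two-sample t-test at 20 v 20, two-sided, has power 0.34 for d = 0.5; 80% power needs d = 0.91. A group-by-time F test with f = d/2 = 0.25 and two time points gives 0.74 to 0.87 for within-woman correlations of 0.3 to 0.5, so the stated 0.80 depends on a test and correlation that the plan does not give. That is a separate matter. Here d = 0.91 serves only as a reference for the cost of losing women.

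**3. Precision.** The documents give no removal rates. Assume 20% on riluzole and 5% on placebo.
- Removed: 0.20 × 20 = 4 and 0.05 × 20 = 1, so 5 of 40, leaving 16 v 19.
- Noncentral t with 33 degrees of freedom and noncentrality d/√(1/16 + 1/19): 80% power needs d = 0.98, up from 0.91.
- At d = 0.91, power falls from 0.80 to 0.74.

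**4. Glutamate effect, retained against all dosed women.** Assume the removed 20% on riluzole would show no effect and the retained women show effect δ.
- All-dosed effect = 0.80 × δ + 0.20 × 0 = 0.80δ.
- Ratio = δ / 0.80δ = 1.25, an overstatement of 25%.
- This is an upper figure for these inputs, because it ignores what the mixed model recovers from the Week 1 scan.

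**5. Selection on outcome, complete cases, no true effect.** Let q be the fraction removed in an arm, z_q the normal quantile, φ the normal density and ρ the correlation between propensity to be removed and a worse Week 8 outcome. The mean of those retained shifts by ρφ(z_q)/(1 − q) SD, and the bias is the difference between arms. For 20% v 5%: 0.280/0.80 − 0.103/0.95 = 0.350 − 0.109 = 0.241, multiplied by ρ.

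| Removed, riluzole v placebo | Bias in SD, ρ = 0.3 to 0.7 | Simulated type I error (nominal 0.05) |
|---|---|---|
| 10% v 10% | 0 | 0.05 |
| 15% v 5% | 0.05 to 0.12 | 0.051 to 0.065 |
| 20% v 5% | 0.07 to 0.17 | 0.055 to 0.081 |
| 30% v 5% | 0.12 to 0.27 | 0.06 to 0.125 |

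The rates and ρ are assumed. The sign follows from assuming that the women removed are those doing worse; if they were doing better, it reverses.

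**The case against.** The case on the other side is substantial.

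- **Nothing is deleted.** A reader might infer that the plan discards the data of poor adherers. It does not: no section removes data already obtained, and Randomization sets aside only women who never took a dose, which suggests that dosed women stay in with whatever data exist. The defect is that later outcomes are not collected. A mixed model uses the Week 1 scan and earlier fatigue forms under missing-at-random. This stands and reduces the problem, but does not remove it if removal tracks unobserved Week 8 values, and no earlier on-treatment cognitive score exists to draw on.
- **Arm dependence is not shown.** The trial is double-blind with an identical-appearing placebo, so discretion can follow arm only through side effects. The side-effect data come from ALS patients and say nothing about adherence. A reader might infer a bias in favour of riluzole; the documents do not settle its direction or existence.
- **Fatigue.** A reader might infer a biased riluzole-versus-placebo fatigue result. Section 10 specifies no such test: Aim 2 models whether change in glutamate predicts change in fatigue. The SD figures above therefore illustrate the mechanism and attach to no listed fatigue comparison.
- **Sample size.** It is tempting to combine unequal removal with a loss of 8 of 40 (16 v 16, detectable d = 1.02). That loss means 20% removed in both arms, and under the same-reason model equal removal gives no bias. The two figures cannot be quoted together.
- **Target of estimation.** For a mechanistic question, the effect while drug is taken is a defensible target, and the 25% figure applies only against an all-dosed target. True, but selection among the retained can bias that target too, and the plan names neither.
- **Over-recruitment.** Participants plans 120 recruits to yield 40 analysable women, whereas Randomization stops at 40 dosed. Whether Week 8 numbers fall below 40 is thus unresolved.

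**Conclusion.** The point holds as a design weakness that should be corrected. As written, the plan permits post-randomisation removal for low adherence and makes no provision to collect Week 8 MRS, fatigue or cognitive outcomes afterwards. That loss can be related to arm and outcome; the documents do not establish that it will be.

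Under the assumed 20% v 5% removal, detectable d rises from 0.91 to 0.98, and the glutamate effect could be overstated by up to 25% relative to all dosed women if those removed would show no effect. Both figures rest on assumed rates, and the second also ignores recovery through Week 1 data. With equal removal for the same reason, there is no bias and only precision suffers.

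**What to change.** Separate study drug from study assessment, without changing any rule on study drug.

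1. In Compliance and in Stopping rules, state that women below 75% adherence who still consent remain in the study for all scheduled assessments, including Week 8 MRS, fatigue forms and cognitive tests.
2. In Section 10, state that every dosed woman is analysed in her randomised arm, and that the subset with at least 75% adherence is a sensitivity analysis.

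The cost is one sentence in each of the three places, plus a few scheduled visits and scans that would otherwise be dropped. The all-dosed estimate may be somewhat diluted by non-adherence; the adherent-subset analysis shows the result without those women, though it carries the selection described above. A Week 8 scan that was not taken cannot be recovered later.
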